7.10 Injection site evaluation

Injection of antibodies has been associated with injection reactions, with onset typically during or shortly after completion of the injection. For this reason, participants will be carefully observed during each injection, and at regular timepoints thereafter.

Injection site checks will be performed at the time points specified in the Schedule of Assessments (Table 4). Participants will be monitored for unusual signs and symptoms of injection site reactions such as pain, localized swelling, tenderness, or erythema. Injection site reactions will be graded as per Table 15. Injection site reactions with a severity grading of moderate or higher will be reported as an AE.

Table 15: Grading of injection site reactions

Mild	Moderate	Severe

• Symptoms may include discomfort,	
• Symptoms may include pain,	
• Ulceration or necrosis• Severe tissue damage

erythema, swelling and itching. • Awareness of symptoms but easily tolerated • Does not interfere with activity • Fully reversible	erythema, swelling and itching • Symptoms severe enough to disturb usual activities and/or sleep. • Treatment/intervention (including analgesia) may be indicated	• Operative intervention indicated • Symptoms incapacitating with inability to work or complete usual activities.
---	---	--

If a participant experiences an injection site reaction, they will continue to undergo unscheduled injection site checks until resolution. Medication to treat symptoms of an injection site reaction (including paracetamol and/or an antihistamine), may be administered per institutional standard at the discretion of the Principal Investigator.

7.11 Pharmacokinetic assessments

Blood samples will be collected at appropriate timepoints to allow serum UPB-101 concentrations and analyses including C_{max} , t_{max} , AUC_{0-t} will be assessed. If appropriate, AUC_{0-inf} , $t_{1/2}$, apparent total body clearance after dosing (CL/F), and apparent volume of distribution during the terminal elimination phase after dosing (Vz/F) will also be analyzed.

7.11.1 PK blood samples

For the timing of individual samples refer to the Schedule of Assessments (Table 4 and Table 5). The date and time of collection will be recorded on the appropriate CRF.

7.12 Pharmacodynamic assessments

Numerous cytokines are involved in the pathogenesis of asthma and several additional biomarkers have been associated with asthma activity (Custovic, Siddiqui et al. 2022). Several approved or in-development asthma medications target cytokines (Lambrecht, Hammad et al. 2019).

Blood samples will be collected at appropriate timepoints to allow asthma-related PD biomarkers to be assessed. CRP and total IgE will be assayed by the central clinical laboratory. The decision to assay the frozen samples will be based on results from earlier sample analyses of [REDACTED]
[REDACTED].

7.12.1 PD blood samples

For the timing of individual samples refer to the Schedule of Assessments (Table 4). The date and time of collection will be recorded on the appropriate CRF.

7.13 Immunogenicity assessments

Blood samples will be collected at appropriate timepoints to allow immunogenicity parameters (ADA, Nabs) to be assessed.

7.13.1 Immunogenicity blood samples

For the timing of individual samples refer to the Schedule of Assessments (Table 4). The date and time of collection will be recorded on the appropriate CRF.

7.14 Volume of blood sampling

The maximum total blood volume collected from participants that take part in this study will not exceed 580 mL overall. The 580 mL permitted in this study is consistent with current clinical practice in Phase 1 studies.

8. ADVERSE EVENTS

The collection, evaluation and reporting of AEs/ARs arising from this clinical study will be performed in accordance with:

- detailed guidance on the collection, verification and presentation of AE/AR reports arising from clinical trials on medicinal products for human use ('CT-3') (2011/C 172/01)
- International Conference on Harmonization (ICH) harmonised tripartite guideline on clinical safety data management: 'Definitions and standards for expedited reporting' E2A
- ICH harmonised tripartite guideline on Development Safety Update Report: E2F
- ICH guideline E2F 'Note for guidance on Development Safety Update Reports (DSUR)'.

It is the Investigator's responsibility to document and report all AEs that occur in the clinical study. The period of observation for collection of AEs extends from the signing of the ICF until the final visit. Additionally, spontaneously reported SAEs will be collected until 30 days after the final study visit. SAEs experienced after this 30-day period will only be reported if the Investigator suspects a causal relationship with the study drug.

8.1 Urgent safety measures

Regulation 30 of the Medicines for Human Use (Clinical Trials) Regulations 2004: SI 2004/1031 specifies that the Sponsor or Investigator may take appropriate urgent safety measures (USM) in order to protect the Participants of a clinical study against any immediate hazard to their health or safety.

Any USMs implemented must be reported to the Sponsor immediately. The Medicines and Healthcare products Regulatory Agency (MHRA) and the Research Ethics Committee (REC) will be notified as soon as possible and in all cases within 3 days.

8.2 Definitions

An '**Adverse Event (AE)**' is any unfavourable and unintended sign (including an abnormal laboratory finding), symptom or disease temporally associated with the use of a medicinal product, whether considered related to it or not.

An AE may be:

- a new symptom or medical condition
- a new diagnosis
- an inter-current illness or an accident
- a worsening of a medical condition/disease(s) that existed before the start of the clinical study
- the recurrence of a disease
- an increase in frequency or intensity of episodic diseases
- a change in a laboratory or other clinical test parameter
 - the criteria to determine whether an abnormal test result should be reported as an AE/AR are as follows. The abnormal test result:
 - is associated with accompanying symptoms, and/or
 - requires additional diagnostic testing or medical/surgical intervention
- an event that leads to a change in study dosing outside of protocol-stipulated dose adjustments, or discontinuation from the study, significant additional concomitant drug treatment, or other therapy, and/or
- considered an Adverse Event by the Investigator or Sponsor.

An AE does not necessarily include the following:

- an abnormal test that needs repeating, in the absence of any of the above conditions. Any abnormal test result that is determined to be an error does not require reporting as an Adverse Event
- surgical procedures themselves are not AEs; they are therapeutic measures for conditions that require surgery. The condition for which the surgery is required may be an AE/AR. Planned surgical measures permitted by the clinical study protocol and the condition(s) leading to these measures are not AEs, if the condition leading to the measure was present before inclusion in the study and has not worsened. In the latter case, the condition should be reported as medical history.

A '**Serious Adverse Event (SAE)**' is defined as any Adverse Event that fulfils any of the following criteria:

- it results in death
- it is life-threatening (the term 'life-threatening' in the definition of 'serious' refers to an event in which the participant was at immediate risk of death at the time of the event; it does not refer to an event which hypothetically might have caused death if it were more severe)
- it requires a hospitalization* or prolongs existing hospitalization

- it results in persistent or significant disability/incapacity
- it is a congenital abnormality/birth defect
- it is considered medically important (medical and scientific judgement should be exercised in deciding whether other AE/ARs are to be considered serious, such as important medical events that may not be immediately life-threatening or result in death or hospitalization* but may jeopardize the participant or may require intervention to prevent one of the other outcomes listed in the definition above. Examples of such events are intensive treatment in an emergency room or at home for allergic bronchospasm; blood dyscrasias; convulsions that do not result in hospitalization; development of drug dependency or drug abuse).

*'Hospitalization' qualifying for an SAE does not include the following: under 24 hours; admission unrelated to an Adverse Event ,e.g., for labour and delivery, cosmetic surgery, social or administrative for temporary placement (e.g., admission due to lack of transport or support at home); admissions for diagnosis or therapy of a pre-existing condition that has not increased in severity or frequency; protocol-specified admission; pre-planned admission; admission to a rehabilitation or nursing facility; hospice; presentation to emergency departments or other urgent care centres; admissions to hospital in-patient facilities for logistical reasons only that did not result in any therapeutic intervention (e.g., awaiting consultation with and decision by senior medical staff or specialists, or for an investigation that is not immediately available); admissions to hospital in-patient facilities for investigation alone and where no significant abnormality was identified and/or no therapeutic intervention was necessary; same-day out-patient surgery.

An '**Adverse Reaction (AR)**' is a response to a medicinal product that is noxious and unintended, which occurs at any dose (in pre-approval clinical experience) or at doses normally used in man for prophylaxis, diagnosis, or therapy of disease or for modification of physiological function (in post-approval clinical experience). The term 'reaction' means that a causal relationship between a medicinal product and an Adverse Event is at least a reasonable possibility. This means that there are facts (evidence) or arguments to suggest a causal relationship.

A '**Serious Adverse Reaction (SAR)**' is any AR that fulfils the criteria of seriousness, as defined above.

A '**Suspected Unexpected Serious Adverse Reaction (SUSAR)**' is a Serious AR that is unexpected. The 'expectedness' of a serious AR is assessed in the light of the Reference Safety Information (RSI).

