^b Symptoms or signs include fatigue, nausea, vomiting, right upper quadrant pain or tenderness, fever, rash and/or eosinophilia (eosinophil percent or count above the ULN).

The treatment group and study Stopping Rules for dose-limiting ARs are described in Table 9 and Table 10 respectively.

Table 9: Treatment group stopping rules

Action	Frequency of dose-limiting ARs	
	Severe	Serious
Dosing of remainder of treatment group (and all other treatment groups of the same or higher dose) to be suspended ^a while dosing of lower dose treatment groups may continue	≥ 2	≥ 1 deemed at least possibly related to the study drug

^a Continuation of dosing requires regulatory approval via a substantial amendment.

Table 10: Study stopping rules

Action	Frequency of dose-limiting ARs	
	Severe	Serious
All dosing suspended ^a		≥1 where SAE deemed at least possibly related to the study drug and is either life threatening or leads to death

^a Continuation of dosing requires regulatory approval via a substantial amendment.

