8.3.4 Expectedness (Reference Safety Information)

No SARs are considered expected by the Sponsor for the purpose of expedited reporting of SUSARs.

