8.7 Potential drug-induced liver injury

Participants with DILI defined as AST or ALT $\geq 3 \times$ ULN; total bilirubin $\geq 2 \times$ ULN; absence of biliary obstruction/cholestasis (alkaline phosphatase $< 2 \times$ ULN) and no other explanation for the findings (e.g., viral hepatitis, chronic or acute liver disease, administration of concomitant hepatotoxic drug) must be reported as an SAE.

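### The and/or in the Section 8.2 hospitalization footnote lets an investigation-only admission that found a significant abnormality drop the hospitalization criterion whenever no treatment was given

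*Protocol*

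**What the plan says.** Protocol Section 8.2 lists the SAE criteria as alternatives: an SAE "is defined as any Adverse Event that fulfils any of the following criteria". One of them is that "it requires a hospitalization* or prolongs existing hospitalization". The asterisk leads to a footnote listing admissions that do not count, which begins "Hospitalization' qualifying for an SAE does not include the following: under 24 hours". Further down, the list excludes "admissions to hospital in-patient facilities for investigation alone and where no significant abnormality was identified and/or no therapeutic intervention was necessary".

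The footnote narrows only the hospitalization criterion. The medically important criterion, in the same section, covers "important medical events that may not be immediately life-threatening or result in death or hospitalization* but may jeopardize the participant", and it rests on medical and scientific judgement. Under Section 8.7, liver injury meeting the definition there "must be reported as an SAE", with or without an admission.

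Section 4.3 says that seriousness overrides severity grade and that the stopping rules apply only to related events. Table 8 counts any adverse reaction meeting a seriousness criterion as a serious dose-limiting reaction. Table 9 suspends a treatment group, and every group at the same or a higher dose, at 1 or more serious reactions "deemed at least possibly related to the study drug" or at 2 or more severe dose-limiting reactions. It has no count for mild or moderate non-serious reactions. Table 10, for the whole study, concerns only related SAEs that are life-threatening or fatal.

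**The concern.** The exemption appears meant for admissions that turned out to be uneventful: the participant was investigated, nothing of note was found, and nothing had to be done. As worded, it also covers the admission where something of note was found, provided it was only investigated. For an investigation-only stay the no-therapy limb is met almost by definition, so the no-abnormality limb screens out almost nothing.

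This matters because several consequences follow from SAE status:

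- SAEs are part of the secondary safety endpoint (Protocol Section 2.2.2, SAP Section 2.2), and the SAP summarises serious events separately (Section 4.10.1).
- Section 8.6 requires notification to the sponsor within 24 hours.
- Section 8.3.4 states "No SARs are considered expected by the Sponsor for the purpose of expedited reporting of SUSARs", so every related SAE is a SUSAR, reportable in 7 or 15 days.
- The Table 9 serious count of 1 depends on it.

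The design puts some weight on these triggers. Section 3.5 has no sentinel dosing and no interim safety review, and allows up to 4 cohorts, so an early participant's event can bear on later dosing.

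**Working it through.** **Inputs.** Footnote wording and SAE criteria: Section 8.2. Liver route: Section 8.7. Thresholds: Section 4.3, Tables 8 to 10. Group size 8, with 4 × 8 = 32 in total: Section 6.2.1. The Table 9 thresholds are fixed rules with nothing behind them to reproduce. The documents give no rate for admissions of this kind.

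**Step 1: logic of the exemption.** Let A = admission for investigation alone, B = no significant abnormality, C = no therapeutic intervention. As written, the exemption is A and (B or C). The strict form is A and B and C. With A true:

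| Abnormality found? | Therapy given? | Exempt as written | Exempt if both required |
|---|---|---|---|
| No | No | Yes | Yes |
| No | Yes | Yes | No |
| Yes | No | **Yes** | **No** |
| Yes | Yes | No | No |

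The third row is the case at issue. The second also differs, but therapy sits poorly with investigation alone. Grouping the words as (A and B) or C exempts the third row too, so the result does not depend on how the sentence is parsed.

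**Step 2: effect on the group stopping count.** Take an event whose only route to seriousness would have been an admission of 24 hours or more:

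| Event | Table 9 count if the admission qualifies | Table 9 count as the footnote is written |
|---|---|---|
| Related, severe under Table 8 | 1 serious suffices | 2 severe needed |
| Related, mild or moderate | 1 serious suffices | none applies |
| Not related | none applies | none applies |

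An event that is also life-threatening, disabling, judged medically important or liver injury under Section 8.7 stays serious, and if related its count stays at 1. In the first row the event still counts as one of the two, so a different severe reaction could complete the pair.

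Table 8 supplies candidates for the first row. ALT or AST above 5 × ULN without raised bilirubin, and an uncorrected QT above 500 ms, are listed as severe and are not serious automatically.

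**Step 3: what the difference between counts of 1 and 2 means, with purely assumed rates.** For a group of 8 and a per-participant probability p of such a related event:

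P(at least 1) = 1 − (1 − p)^8

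P(at least 2) = 1 − (1 − p)^8 − 8p(1 − p)^7

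| Assumed p | P(at least 1) | P(at least 2) |
|---|---|---|
| 1% | 7.7% | 0.3% |
| 5% | 33.7% | 5.7% |
| 10% | 57.0% | 18.7% |
| 20% | 83.2% | 49.7% |

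At p = 1%: 0.99^8 = 0.9227, so P(at least 1) = 0.0773. Also 8 × 0.01 × 0.99^7 = 0.0746, so P(at least 2) = 0.0027.

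These figures show how the two thresholds behave and do not forecast events. Rates of 5% to 20% are implausible in healthy volunteers for whom Section 3.5 anticipates no adverse drug reactions. The last column also requires every such event to be graded severe and no other severe reaction to contribute.

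**The case against.** The strongest reply is that the protocol already catches these events elsewhere. The asterisk also appears inside the medically important criterion, so that criterion expressly takes in events that fail the hospitalization footnote. This is right, and it limits the point: an automatic trigger is lost, and a judgement-based one remains. It does not remove the point, because two assessors can judge the same admission differently, whereas a stay of 24 hours or more leaves little to judge.

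Second, such admissions should be few. Participants are in-house to Day 15 and the stay can be prolonged case by case (Table 6), so separate hospital admissions would arise mainly afterwards. A stay managed by observation is also arguably monitoring and so outside the exemption. Both arguments reduce frequency. The second itself turns on how an assessor reads the footnote.

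Third, there are backstops. Section 3.5 allows suspension for any safety concern, and Section 4.2 provides for an ad hoc safety review. In a single-dose study, events seen after a group is fully dosed leave nothing in that group to suspend. All true, but the backstops are discretionary and do not restore SAE or SUSAR reporting.

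Fourth, the neighbouring exemption for logistical admissions without therapy has no condition on abnormal findings either, so changing one word does not tidy the whole footnote. That is fair, and is taken up in the fix.

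**Conclusion.** The point holds in limited form. The wording makes one of the exemption's two conditions almost idle, and the affected event loses a near-objective SAE criterion.

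Two stronger readings are tempting. A reader might infer that such an admission cannot be an SAE. The documents do not support that, because the footnote qualifies one criterion out of several alternatives and the others still apply. A reader might also infer that the count needed to suspend dosing rises from 1 to 2 in general. That is true only for a related reaction that is graded severe and meets no other seriousness criterion. For a mild or moderate one the effect is larger, since no count applies. For an unrelated one there is no effect. Whole-study suspension under Table 10 does not change.

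The size is therefore a change of rule for a rare class of event, and no defensible probability can be put on it from these documents. The conclusion rests on the literal reading of *and/or*. If the sponsor intended both conditions, the text does not say so. It is worth correcting, but it does not threaten the study.

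**What to change.** In the investigation-only exemption of the Section 8.2 footnote, replace *and/or* with *and*, so that both conditions must hold before the admission is disregarded. This edits a reporting definition. The Table 9 and Table 10 thresholds stay as they are.

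In the same edit, reconcile the footnote with the seriousness criteria that Tables 8 and 9 rely on. Section 4.3 currently sends the reader to Section 8.1 for those criteria, but they are in Section 8.2. The sponsor should also confirm whether the neighbouring logistical exemption is meant to apply when a significant abnormality has been found.

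The drafting cost is one word and a cross-reference. In operation it may produce an occasional extra SAE report. If the event is related, it may also bring a suspension under the existing Table 9 rule, and resuming dosing then needs regulatory approval through a substantial amendment. That is a real cost when it occurs, but it should be rare in a study of this size.

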8.3 Classification

8.3.1 Assessment of severity

The Investigator will assess the severity of AE/ARs using a categorical grading (mild, moderate or severe) with grading of individual AE/ARs based on global clinical assessment undertaken by an appropriately delegated Research Physician.

Changes in the severity of an AE/AR should be documented to allow an assessment of the AE/AR duration at each level of severity. AE/AR characterized as intermittent require documentation of the start and end of each incidence. Table 16 below guides categorical grading of AE/ARs.

Table 16: Categorical grading of AE/ARs

Grade	Global clinical assessment & application of grading to a diagnosis
Mild	Overall clinical condition is asymptomatic, or symptomatic with all the following characteristics: 
• no or minimal interference with usual social and/or functional activities• no impact, or minimal impact (e.g., of short duration or a return to normal status without intervention), upon usual self-care activities• deviation from reference range for the population and from the participant's clinically determined physiological baseline has no clinical impact and does not signal potential safety concern or unanticipated clinical risk• the condition is reversible to baseline within an anticipated timeframe• intervention or treatment is either not indicated or indicated only to increase participant's sense of wellbeing and comfort, but not due to safety concerns or risk.
Moderate	Overall clinical condition is asymptomatic or is symptomatic with no or minimal impact on usual self-care activities and one or more of the following characteristics: 
• greater than minimal interference with usual social and functional activities• deviation from reference range for the population and from the participant's baseline has clinical impact, but there is no acute safety concern or unanticipated risk. However, should the condition persist and/or occur more frequently, it could signal a potential safety concern or unanticipated risk and should therefore be monitored• reversibility of the condition to baseline condition takes longer than desirable or anticipated, impacting on the participant's wellbeing beyond the mere severity of the condition• further medical assessment, intervention or treatment indicated to increase participant's sense of wellbeing and comfort and to accelerate recovery and/or to prevent worsening.
Severe	Overall clinical condition is asymptomatic or is symptomatic with one or more of the following characteristics: 
• significant impact on usual self-care activities• inability to perform usual social and functional activities• the deviation from reference range for the population and from the participant's baseline has significant clinical impact, it is an acute safety concern or unanticipated risk and requires close and continuous monitoring• the reversibility of the condition to baseline condition takes significantly longer than desirable or anticipated, with significant impact on the participant's wellbeing• intervention or treatment essential to treat the acute manifestations and to prevent worsening• life-threatening or actually leads to death.

